The primary analysis model will be a random effects logistic regression, implemented through the SAS Glimmix procedure. Timely follow-up (yes/no) will be the patient-level outcome and random effects for practice and physician will allow for exchangeable correlation between patients seen within the same practice and by the same physician. The primary fixed predictors will be 3 indicator variables representing the 3 intervention arms and we will use a global likelihood ratio test to compare the 4 study arms. If the global test is significant ($p < 0.05$), we will compare the intervention arms to the control group (our primary comparisons with a Bonferroni-adjusted significance level of 0.0167) and to each other (secondary comparisons). Comparisons to the control arm will capture the cumulative effects of the interventions, while comparisons between the intervention arms will capture the marginal effects of each level of intervention. We will include covariates for the type of cancer, level of initial screening abnormality, and any patient, provider or practice characteristics which are identified as confounders.

Results will be presented as adjusted follow-up rates, with 95% confidence intervals, calculated using marginal standardization.

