In discussions (but not in the protocol), there was interest in exploring how COVID affected the outcome, in the sense that patients who became eligible when COVID was more prevalent (and elective care was less available) may have taken longer to have follow-up. Because this is a complicated topic and will distract from the main randomized results, it was decided to save such analyses for a subsequent manuscript. The current manuscript will simply adjust (through indicator variables) for 3-month time windows. Since COVID peaked in different areas at different times, these indicator variables will be included as interactions with study site (Boston versus Dartmouth).

Contents:

1. Exhibit 1: Figure 1: Consort Diagram
2. Exhibit 2: Table 1: Baseline Characteristics, by Arm
 - a. Patient characteristics
 - i. Sex
 - ii. Age
 - iii. Race/Ethnicity
 - iv. Primary insurance
 - v. Primary language
 - vi. Marital status
 - vii. Comorbidities
 - viii. Number of PCP visits in prior year
 - ix. Number of no show visits in prior year
 - x. Type of cancer
 - xi. Severity of screening abnormality
 - xii. Rurality (distance or population)
 - xiii.
 - b. PCP characteristics (from protocol; none currently in the prototype table):
 - i. Sex
 - ii. Provider type (MD/ DO, NP/ PA, other)
 - iii. Specialty
 - iv. Panel size (not risk adjusted)

- c. Clinic characteristics (from protocol; none currently in the prototype table):
 - i. Location (hospital; community health center)
 - ii. Visit volume at time of randomization
 - iii. Patient mix (% female; % Medicaid) at time of randomization

- 3. Exhibit 3: Table 2: Overall Primary (120 day completion) and secondary (240 day) outcome analyses
Intent-to-Treat and Modified Intent-to-Treat;
“Unadjusted” and Adjusted
 - a. Presentation: Data will be shown by arm, both ITT and mITT, both adjusted and “unadjusted”
 - i. The overall global p-value (<0.05) for the adjusted ITT analysis will be shown. If the global test is significant, then three pairwise tests (each arm against control/Arm 1) looking for $p<0.0167$.
 - ii. All other analyses and comparisons will be based on 95% confidence intervals

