 - b. Primary and secondary analyses: SAS Proc GLIMMIX with the patient as the unit of analysis and a binary outcome (completed/not completed). All models (including “unadjusted”) will include random effects for practices and physicians. All models (including “unadjusted”) will include fixed effects for type of cancer. All models (including “unadjusted”) will include indicator variables for time (calendar month), along with interaction terms with site (Boston versus Dartmouth).
 - i. Unadjusted analysis: The model above will include random effects for practices and physicians, fixed effects for cancer types, fixed effects and interactions for calendar month and study stie, and indicator variables for Arms 2, 3, and 4.

 - ii. Adjusted analysis: The covariates from 2 above will be added individually to the model. Any that are significant at $p<0.05$ and change the coefficient of any of the 3 indicators for treatment arm by $>20\%$ will be retained in the model as confounders. (Type of cancer and calendar month will be retained in the model regardless of significance or confounding.) Adjusted completion rates will be calculated by marginal standardization and presented in the Table.

- 4. Exhibit 4: Figure 2: Forest plot with subgroup analyses for the primary (120 day completion) outcome

Intent-to-Treat
Adjusted only

- a. Presentation: Data will be shown by subgroup as an odds ratio (versus the control arm 1) with 95% confidence interval; ITT; adjusted only
 - i. P-values for interaction will be presented
 - ii. All other comparisons will be based on 95% confidence intervals
- b. Subgroup analyses: SAS Proc GLIMMIX with the patient as the unit of analysis and a binary outcome (completed/not completed). All models will include random effects for practices and physicians. All models will include fixed effects for type of cancer and calendar month.
 - i. Subgroups (each set analyzed separately):
Type of cancer (breast; cervical; CRC; lung)
Severity of abnormality (low; medium; high)
 - ii. Adjusted analysis: The model above will include random effects for practices and physicians, fixed effects for cancer types and calendar month, indicator variables for Arms 2, 3, and 4, indicator variables for the subgroups, and interaction terms for the arms-by-subgroups.
A global test for effect modification will be run and reported. However, regardless of significance, a separate “unadjusted” model will be run for each subgroup.

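### Covariates for the primary model are selected on the outcome data, so the model depends on the observed effect and the 5% level of the global test is not guaranteed

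*Combined protocol and SAP*

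**What the plan says.** SAP 3.a.i (Exhibit 3, Table 2) names the model that carries the primary test: "The overall global p-value (<0.05) for the adjusted ITT analysis will be shown". Only if that test is significant are Arms 2, 3 and 4 each compared with Arm 1, at 0.0167.

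SAP 3.b.ii says how that model is built: "The covariates from 2 above will be added individually to the model". The list meant is Exhibit 2, which holds patient, PCP and clinic characteristics. The clinic items are location, visit volume, % female and % Medicaid. Two conditions must both hold for a covariate to stay. The first is p<0.05 ("Any that are significant at"). The second is that it would "change the coefficient of any of the 3 indicators for treatment arm by" more than 20%. Only cancer type and calendar month are exempt. The Cox model (SAP item 5.c) takes over the same adjustment set.

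The protocol's Analysis Plan specifies the form of the test: "we will use a global likelihood ratio test to compare the 4 study arms". It also says that level of screening abnormality will be a covariate. The protocol's randomization section stratifies on practice size, % female and % Medicaid. SAP 3.b.ii forces none of these four variables into the model.

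**The concern.** Both conditions are judged on the outcome data, and the second uses the observed arm coefficient as its yardstick. If any one of the three coefficients is near zero, a very small shift exceeds 20% of it and the covariate passes. If all three are large, the same shift falls short and the covariate is left out. What is called the adjusted model therefore reflects the size of the observed effect as well as confounding. The final p-value makes no allowance for the choice.

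Two things are at stake. One is the 5% level of the global test, which is the trial's first decision. The other is precision: the rule tends to discard prognostic covariates in just the situation where the intervention works.

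**Working it through.** **The plan's own figures.** The pairwise level reproduces: 0.05/3 = 0.0167. For the sample size, take 50% vs 61% (the control rate is the protocol's background average, so an assumption here), two-sided 0.0167 and 80% power:

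n = [2.394 × √(2 × 0.555 × 0.445) + 0.842 × √(0.5 × 0.5 + 0.61 × 0.39)]² / 0.11² = about 426 per arm.

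The planned 831 per arm implies a design effect of 831/426 = 1.95. With 3324/44 = 75.5 patients per practice, the ICC is 0.95/74.5 = 0.0128. The documents state no ICC, so this is consistent with the plan but does not verify it. It is the value assumed below.

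**How the 20% yardstick behaves.** Take a patient covariate with log OR 0.25 per SD and covariate ICC 0.05, in 11 practices per arm of 75 patients (assumed).
- Variance of a practice mean: 0.05 + 0.95/75 = 0.0627. SD of the arm difference: √(2 × 0.0627/11) = 0.107. SD of the shift in an arm coefficient: 0.25 × 0.107 = 0.027.
- No effect: the SE of an arm log OR is √(1.95 × 2/(831 × 0.25)) = 0.137, so its median absolute value is 0.6745 × 0.137 = 0.092. The bar is 0.2 × 0.092 = 0.018, below the typical shift, and passing for any one of three arms is enough.
- Effect of 11 points: log OR = ln(0.61/0.39) = 0.45. The bar is 0.09, about 3.4 times the typical shift.

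A patient-level binary simulation agrees. The rule kept about 5 of 10 truly prognostic covariates under no effect, and 0.7 of 10 when all arms worked by 11-14 points.

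**Type I error.** This was a Gaussian random-intercept stand-in for the logistic model, with 44 practices and 8,000-12,000 null trials per setting (Monte Carlo SE about 0.2 points). The table gives global rejection in %, using a REML F test with practice-level degrees of freedom.

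| Candidates | None | SAP rule | p<0.05 only | >20% only | All fixed |
|---|---|---|---|---|---|
| 10 strong patient-level, covariate ICC 0.05 | 5.3 | 4.9 | 5.5 | 4.9 | 5.5 |
| 10 strong patient-level, covariate ICC 0.2 | 5.3 | 4.1 | 5.3 | 4.1 | 5.3 |
| Mixed patient-level, 2 prognostic clinic items | 5.4 | 6.5 | 6.7 | 5.5 | 5.2 |
| Same, 272 per practice (about 12,000 patients) | 5.2 | 5.5 | 5.5 | 4.8 | 4.4 |
| 14 patient-level, 5 clinic items (3 prognostic) | 5.1 | 6.7 | 7.0 | 5.3 | 4.6 |

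A setting with weak patient-level effects gave 6.0% under the rule. Separate linear practice-mean simulations gave 5.7-8.2% with practice-level candidates and 4.9% with patient-level candidates only. Forcing all covariates gave 4.8-5.2%.

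**Family-wise error.** In a linear version with 20,000 trials, a false arm-versus-control claim (global p<0.05, then 0.0167) occurred in 3.2% with no covariates, 4.4% under the rule and 3.3% with all forced.

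**Power for Arm 4, all arms working.** The patient-level simulation gave 82% with no covariates, 85% with the rule and 90% with 10 prognostic covariates forced. Linear versions gave 88% vs 92%, and 84% vs 88% with 18 candidates. Further runs gave 85-90% with the rule and 92-93% forced. The loss is roughly 3-8 points. Screening on p alone did not lose it. Forcing many weak practice-level covariates gave no gain.

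**The protocol's likelihood ratio test.** In the random-intercept settings it rejected in 6.5-7.2% with no selection, 5.6-9.8% with the rule and 6.1-10.0% with all covariates fixed. Across all runs with fixed covariates the range was about 6-12%.

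**The case against.** A reader might infer that the 20% criterion by itself pushes the global error to 6-7%. That does not follow. The documents give neither an ICC nor covariate strengths, so no single figure is a property of the SAP. With strong patient-level covariates, where only the 20% criterion selects, there was no excess. In the mixed and clinic-item settings of the table, the p<0.05 screen alone did as much as the full rule or more. The 20% criterion is not always harmless: alone it gave 6.2% in the weak-effect setting and 6.0-6.7% in some linear runs.

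The simulations are also simplified. They have no physician effects and no calendar-by-site terms, and the random-intercept runs have equal practice sizes and no stratification. Stratifying on practice size, % female and % Medicaid should limit imbalance in the very practice-level variables that drive the excess. This stands as a reason not to rely on the upper end of the range.

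Fixing the covariates does not restore 5% under the likelihood ratio test that the protocol names. This stands too, and it changes the remedy.

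Finally, false claims in the primary comparisons stayed below 5% in the runs that reported them, Arm 4 power under the rule stayed above the planned 80%, and Table 2 shows the less adjusted model alongside. These limit the severity. They do not make an outcome-driven primary model preferable to a fixed one.

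**Conclusion.** The concern holds in a limited form. The rule makes the primary model depend on the observed effect, so the 5% level is not guaranteed. With 44 practices of 75 patients, ICC about 0.013 and a small-sample F test, null rejection is about 4-5% with strong patient-level candidates only and about 5.5-8% with practice-level candidates, which Exhibit 2 contains. The p<0.05 screen is at least as responsible as the 20% criterion. The power loss of roughly 3-8 points does belong to the 20% criterion, and it is measured against forcing covariates that are truly prognostic. All of these sizes rest on assumed inputs.

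Two points need no simulation. The SAP leaves severity to selection although the protocol says it will be included, and it does not force the stratification factors. The SAP should be changed, but the defect does not invalidate the trial.

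**What to change.** Replace the selection sentence in SAP 3.b.ii with a short set named before any arm coefficient is seen: cancer type, calendar time by site, severity, the three stratification factors, and a few patient covariates chosen on prognostic grounds. Retain them regardless of p-value or coefficient change. Use the same set for 120 and 240 days, ITT and mITT, and the Cox model. Keep the 20%-change model as a labelled sensitivity analysis.

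Also replace the likelihood ratio test with a global test that uses small-sample, practice-level denominator degrees of freedom.

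The cost is mainly wording. There are a few more fixed parameters at practice level, so that part of the list should stay short. The clinic variables must also be added to the analysis dataset: the SAP says that none are currently in the prototype table, and the protocol's list of data elements sent for analysis names none. The protocol already reports that the study has ended. If arm coefficients have been seen, the fixed-set model should be reported as specified afterwards.

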Inclusion criteria: Individuals who have an abnormal screen that is due for follow-up including:

- Breast: women 40-80 years with an *incident* (i.e., newly detected) abnormal screening mammogram or digital breast tomosynthesis (DBT) exam.
- Cervical: women 21-65 years with an *incident* abnormal screening Pap.

- Colorectal: adults 40-80 years with an abnormal screen, including *incident* FOBT/ FIT, or *prevalent* colonoscopy. Because of the long periods of time required for follow-up of colonoscopies, we will look back over a 5-year period and will therefore find *prevalent* abnormalities that become due for follow-up.
- Lung: adults 55-80 years, current and former smokers, with an *incident* abnormal LDCT result.

Definition of the specific screening abnormalities and timing of diagnostic evaluation are based on our prior work, expert opinion, and the literature. Need for follow-up will be determined by the lack of an appropriate clinical test within the specified time as documented in the EHR.

Exclusion criteria: We will exclude patients who: 1) are not English or Spanish-speaking, or 2) have had prior cancer of the organ for each screening test (i.e., women with prior breast cancer will not be tracked for breast cancer screening abnormalities) as these individuals may have non-standard follow-up care recommendations.

Intervention Design and Randomization Scheme. We will perform a 4-arm cluster RCT with randomization done at the practice-level, across the participating practices. We have chosen this level of randomization as it would be logistically complicated for the practices to have different patients randomized to different intervention components (i.e., reduced contamination). While we have received the approval of the primary care network leadership of the participating networks and have discussed the study with practice leadership, practices will be given the opportunity to opt-out of the study before practices are randomized. Randomization will be stratified based on: (1) practice size, (2) percent female, and (3) percent of patients on Medicaid as a marker for socioeconomic status.

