Since, some of the subgroup sample sizes will be limited, not all the covariates from the primary overall model above in (3) will be added to each stratified models. Decisions will be made based on the degree of confounding and the sample size.
- c. Appendix: A similar figure will be created for the mITT data. A decision of whether to display it in the appendix will be made based on the findings.

5. Exhibit 5: Figure 3: Kaplan-Meier Curves

- a. Four curves (4 arms), unadjusted, ITT
- b. Log-rank p-value
- c. A Cox regression model will be built for the ITT data. Since only one level of clustering is available, the model will use the analogue of random effects for practices and adjust for the same variables as in the logistic regression model above.
 - i. Significance testing will use a global p-value across all 4 arms and, if significant at $p<0.05$, pairwise comparisons between each arm and the control arm will be carried out. Results for the pairwise comparisons will be presented as 95% confidence intervals.
 - ii. The results of the Cox regression will be reported in the text. A table of the model results may appear in the Appendix.

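### The log-rank p-value on Figure 3 ignores the randomisation of practices and will tend to be too small if outcomes stay correlated within practice after stratification

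*Combined protocol and SAP*

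**What the plan says.** The protocol (Intervention Design and Randomization Scheme) states: "We will perform a 4-arm cluster RCT with randomization done at the practice-level". It adds: "Randomization will be stratified based on: (1) practice size, (2) percent female, and (3) percent of patients on Medicaid". Recruitment Procedures puts the number of practices at no more than 44.

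SAP item 5 (Exhibit 5, Figure 3) plans, in 5.a, "Four curves (4 arms), unadjusted, ITT" and, in 5.b, "Log-rank p-value". Item 5.b says nothing else: no variance estimator, no clustering term, no permutation scheme.

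Clustering enters Exhibit 5 only in 5.c, the Cox model, where "the model will use the analogue of random effects for practices". Item 5.c.i says "Significance testing will use a global p-value across all 4 arms", and 5.c.ii says "The results of the Cox regression will be reported in the text", with a model table that may or may not go in the appendix.

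Time to completion is one of the two secondary outcomes listed in SAP item 2. The protocol's plan for it (Analysis Plan/ Sample Size) is a clustered proportional hazards model; no log-rank test is mentioned.

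**The concern.** The standard log-rank variance is valid when patients are independent. Here whole practices were allocated. If patients of the same practice resemble one another in how soon they are followed up, arms differ by chance more than that variance allows, and the p-value is too small.

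The plan recognises this elsewhere. The protocol's primary model allows for correlation within practice and within physician. In the SAP, even the logistic models labelled unadjusted carry practice terms; item 3.b.i reads "Unadjusted analysis: The model above will include random effects for practices and physicians". So unadjusted does not mean unclustered elsewhere in this SAP, and the log-rank test is the one comparison of follow-up between arms with no practice term.

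What is at stake is the reading of a named secondary outcome. Figure 3 could carry a small p-value for an arm difference that the plan's own clustered Cox test does not support, and a reader may look at the figure before the text.

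**Working it through.** **Inputs from the documents.** Planned N = 3324, about 831 per arm (protocol, Patient Identification and Enrollment); at most 44 practices (Recruitment Procedures); stratified allocation of practices. Mean practice size is 3324/44 = 75.5.

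**Inputs that are missing.** The documents give no ICC, no distribution of practice sizes, no number of strata and no share of practice variance explained by the strata. All are assumed below.

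**Is the ICC range reasonable?** The planned 831 per arm cannot be reproduced, because the protocol states neither the control rate nor the ICC behind it. It gives only a bound of sorts. For an 11-point difference at 80% power, with control rates of 30% to 50% and no clustering, the usual two-proportion formula gives:

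- at α = 0.0167, 395 to 432 per arm. The implied design effect is 831/432 = 1.92 to 831/395 = 2.10, and ICC = (DEFF − 1)/(75.5 − 1) is about 0.012 to 0.015;
- at α = 0.05, 296 to 324 per arm, so a design effect of 2.6 to 2.8 and an ICC of about 0.021 to 0.024.

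If clustering accounts for the gap, the sponsor allowed for an ICC near or slightly above the upper part of the range 0.005 to 0.02 used here.

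**Simulation under no arm effect.** The assumed layout is 44 equal practices in 11 strata of four, one practice per arm in each stratum. Follow-up times are exponential with 50% complete by day 120, and each practice has a normal effect on the log hazard with standard deviation SD. With half complete at day 120, the ICC of the 120-day outcome is about (ln 2)² × SD² = 0.48 × SD², so SD = 0.102, 0.145 and 0.206 give ICC 0.005, 0.01 and 0.02. A share s of the log-hazard variance is common to the stratum. The 3-df log-rank test is taken at nominal 5%, with 4000 runs (2000 for s = 1) and a Monte Carlo standard error of at most 0.008. With ICC 0 the test rejects in 5.3% of runs.

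Rejection rate, censoring at day 240:

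| Share explained by strata | ICC 0.005 | ICC 0.01 | ICC 0.02 |
|---|---|---|---|
| none | 16.8% | 29.2% | 50.1% |
| half | 10.8% | 17.0% | 29.8% |
| 90% | 6.3% | 7.4% | 9.5% |
| all | 5.2% | 5.7% | 5.0% |

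The protocol censors at end of study. With censoring times taken as uniform from 240 to 970 days (240 days plus an assumed two years of accrual):

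| Share explained by strata | ICC 0.005 | ICC 0.01 | ICC 0.02 |
|---|---|---|---|
| none | 21.1% | 37.3% | 57.1% |
| half | 12.0% | 21.6% | 35.1% |
| 90% | 6.0% | 7.2% | 9.4% |

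**Checks.**

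- The binary-outcome design effect, 1 + 74.5 × ICC = 1.37, 1.75 and 2.49, gives P(χ²₃ > 7.815/DEFF) = 0.128, 0.214 and 0.371. This is lower than the first row of the first table because it uses the 120-day ICC, whereas the log-rank test gathers events to day 240.
- By day 240, 75% are complete, which is 75.5 × 0.75 = 56.6 events per practice. An inflation of 1 + 56.6 × SD² gives 0.178, 0.312 and 0.513, in line with the simulated row.
- Separately written code at ICC 0.0128, with 2000 runs and censoring at day 240, gives 37%, 28%, 17%, 8% and 5.1% for shares of 0, 30%, 60%, 90% and 100%.

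**Enrolment above 3324.** The protocol allows up to 12,000 patients, or 12,000/44 = 273 per practice. With no benefit from strata, the rejection rate at ICC 0.005 is then 48%.

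**The permutation alternative.** A log-rank test that permutes practices within strata (399 permutations, 2000 runs) rejected in 4.1% to 5.8% of runs over shares 0, 50%, 90% and 100% and all three ICCs.

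**The case against.** The strongest reply is that little depends on this p-value. Item 5.c.i names the practice-clustered Cox test as the significance test for time to follow-up, no threshold or decision is attached to the log-rank test, and the 120-day and 240-day analyses carry practice and physician random effects. All of that stands, and it limits the point to one annotation. It does not make the annotation valid, and the annotation is what the figure would show.

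Second, item 5.b is merely silent; a clustered or permutation version is not excluded. True, but a log-rank p-value named without qualification beside unadjusted curves, followed by a separate line that handles clustering for the Cox model only, reads as the ordinary test. If a clustered version was meant, naming it settles the matter.

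Third, the size is assumed. The range runs from nominal to severe, the 11 strata of four and equal practices are inventions, and reading the two-year trial duration as an accrual period is an assumption. This also stands: the percentages show sensitivity and do not estimate this trial's error. The direction does not depend on the layout. Nothing in the documents shows that three practice-level factors absorb nearly all the practice variance, which is what a nominal error rate would need.

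Finally, a covariate-adjusted Cox p-value on unadjusted curves is a mismatch that a label discloses but does not remove. That is fair, and it is a reason to consider deletion or the permutation test.

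**Conclusion.** The point holds. On its plain reading, item 5.b prints a p-value that is not valid for a trial that randomised practices, and the rest of the plan does not make that mistake. The true size of the nominal 5% test would be about 6% to 10% if the strata explain 90% of the practice variance, 11% to 30% if they explain half, and 17% to 50% if they explain none, for ICCs from 0.005 to 0.02, N = 3324 and censoring at day 240. It would be close to 5% only if there were no residual correlation within practice. These figures rest on the assumed ICC, strata and equal practice sizes. The error is confined to the Figure 3 annotation; the primary conclusion and the planned Cox inference are untouched. It should be corrected because it concerns a named secondary outcome and the correction costs almost nothing.

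**What to change.** Amend item 5.b in one of three ways:

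- delete the p-value and label the curves descriptive;
- print the global arm p-value from the practice-clustered Cox model of 5.c, labelled as adjusted;
- if an unadjusted test is wanted, specify a practice-level one, such as a log-rank test that permutes practices within the randomisation strata.

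The change is one line of the SAP and needs no new data. The first two options need no extra analysis; the third needs one more test and the list of strata. The price is that the printed p-value will usually be larger, or absent.
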